##### *Starting weekly dose*

The second dose is the starting weekly dose which is equal to the pre-study total daily basal insulin dose multiplied by 7. The dose will be equivalent to pre-study basal insulin doses, with further adjustment for participants who used insulin glargine U-300 or NPH as their pre-study basal insulin. Details on deriving the starting weekly dose are described in Section [6.5](#).

##### *Dose adjustments*

Dosing will be individualized based on FBG and hypoglycemia events in the prior week, and adjustments may occur weekly from Visit 5 to 15 (Week 2 to 12) and then every 4 weeks thereafter, or more often as clinically indicated.

##### **Insulin glargine**

Insulin glargine will be titrated to achieve the FBG target using an algorithm that is patterned after the well-established Riddle algorithm (Riddle et al. 2003) but modified to balance efficacy and hypoglycemia risk for the same FBG targets as LY3209590.

***Starting dose***

The starting dose of insulin glargine is designed to be equivalent to the pre-study basal insulin dose, with further adjustment for participants who used insulin glargine U-300 or NPH as their pre-study basal insulin. Details on deriving the starting weekly dose are described in Section 6.5.

***Dose adjustments***

Dosing will be individualized based on FBG and hypoglycemia events in the prior week and adjustments may occur weekly from Visit 4 to 15 (Week 1 to 12) and then every 4 weeks thereafter, or more often as clinically indicated.

**4.4. End of Study Definition**

The end of the study is defined as the date of the last scheduled procedure shown in the SoA for the last participant in the study.

A participant is considered to have completed the study if the participant has completed all periods of the study including the last scheduled procedure shown in the SoA.

## 5. Study Population

Prospective approval of protocol deviations to recruitment and enrollment criteria, also known as protocol waivers or exemptions, is not permitted.

### 5.1. Inclusion Criteria

Participants are eligible to be included in the study only if all of the following criteria apply:

#### Age

1. Are 18 years of age or older, at screening (Visit 1), per local regulations.

#### Type of participant and disease characteristics

2. Have a diagnosis of T2D according to the WHO criteria, currently treated with basal insulin and at least 2 injections of prandial insulin per day.
3. Are receiving  $\geq 10$  units of total basal insulin per day at screening (Visit 1).
4. Are receiving  $\leq 2$  units/kg/day of total daily insulin at screening (Visit 1).
5. Have an HbA1c value of 7.0% to 10%, inclusive, as determined by the central laboratory at screening (Visit 1).
6. Have been treated with a stable regimen of one of the following basal insulins used according to local product label with or without noninsulin diabetes therapy for at least 90 days prior to screening (Visit 1).
  - once daily U-100 or U-200 insulin degludec
  - once daily U-100 or U-300 insulin glargine
  - once or twice daily U-100 insulin detemir (Levemir® [Novo Nordisk A/S., Bagsvaerd, Denmark]), or
  - once or twice daily human insulin Neutral Protamine Hagedorn.
7. Have been treated with at least twice daily dosing of any of the following insulins used according to local product label for at least 90 days prior to screening (Visit 1). One dose of prandial insulin must occur at the evening meal.
  - Insulin lispro (U-100 and U-200)
  - Insulin lispro-aabc (Lyumjev™ [Eli Lilly and Co., Indianapolis, IN], U-100 or U-200)
  - Insulin aspart (U-100; including Fiasp® and NovoLog® [Novo Nordisk A/S., Bagsvaerd, Denmark])
  - Insulin glulisine (U-100), or
  - Regular insulin (U-100).
8. Acceptable noninsulin diabetes therapies may include 0 to up to 3 of the following with a stable dose for at least 90 days prior to screening (Visit 1).
  - dipeptidyl peptidase IV inhibitors

- sodium-glucose co-transporter-2 inhibitors
- biguanides (for example, metformin), or
- glucagon-like peptide-1 receptor agonists.

Note: All noninsulin diabetes therapies must be used in accordance with the corresponding local product label at the time of screening (Visit 1), and participants should be willing to continue stable dosing throughout the study according to the protocol.

### **Weight**

9. Have a body mass index  $\leq 45 \text{ kg/m}^2$ .

### **Sex and contraceptive/barrier requirements**

Contraceptive use by participants should be consistent with local regulations regarding the methods of contraception for those participating in clinical studies.

10. Male study participants: No male contraception required except in compliance with specific local government study requirements.

Female study participants: For the contraception requirements of this protocol, see Section [10.4](#).

### **Study procedures**

11. In the investigator's opinion, are well-motivated, capable, and willing to

- self-inject treatment, as required for this protocol; visually impaired persons who are not able to perform the injections must have the assistance of a sighted individual trained to inject the IP; persons with physical limitations who are not able to perform the injections must have the assistance of an individual trained to inject the IP
- adhere to the study basal-bolus insulin MDI regimen and use of study insulins according to injection instructions and protocol
- use LY3209590 or insulin glargine, and insulin lispro
- use the glucometer supplied for this study for glucose monitoring, diabetes management, and data collection per protocol
- wear blinded CGM during specified periods
- maintain an electronic study diary as required for the protocol, and
- must have a normal wake/sleep pattern, such that midnight to 0600 hours will reliably reflect a usual sleeping period.

### **Informed consent**

12. Capable of giving signed informed consent as described in Section [10.1.3](#), which includes compliance with the requirements and restrictions listed in the ICF and in this protocol.

## 5.2. Exclusion Criteria

Participants are excluded from the study if any of the following criteria apply:

### Medical conditions

#### *Diabetes related*

13. Have a diagnosis of type 1 diabetes mellitus or latent autoimmune diabetes, or specific type of diabetes other than T2D (for example, monogenic diabetes, diseases of the exocrine pancreas, drug-induced or chemical-induced diabetes).
14. Are currently receiving any of the following insulin therapies anytime in the past 90 days:
  - insulin mixtures
  - AfreZZa® (insulin human) inhalation powder (MannKind Corporation, Danbury, CT), or
  - continuous subcutaneous insulin infusion therapy
  - regular insulin U-500
15. Have a history of greater than 1 episode of ketoacidosis or hyperosmolar state/coma requiring hospitalization in the 6 months prior to screening (Visit 1).
16. Have had any episodes of severe hypoglycemia, defined as requiring assistance due to neurologically disabling hypoglycemia, within the 6 months prior to screening (Visit 1).
17. Have hypoglycemia unawareness in the opinion of the investigator.
18. Anticipate making changes in personal CGM or FGM use (for example, initiation, stopping, or changing device) during the study.

#### *Cardiovascular*

19. Have had New York Heart Association Class IV heart failure or any of the following cardiovascular conditions in the past 3 months prior to screening (Visit 1): acute myocardial infarction, cerebrovascular accident (stroke), or coronary bypass surgery.

#### *Gastrointestinal*

20. Have undergone gastric bypass (bariatric) surgery, restrictive bariatric surgery, for example Lap-Band, or sleeve gastrectomy within 1 year prior to screening (Visit 1).
21. Have presence of clinically significant gastroparesis in the opinion of the investigator.

#### *Hepatic*

22. Have acute or chronic hepatitis, cirrhosis, or obvious clinical signs or symptoms of any other liver disease, except NAFLD (that is, persons with NAFLD are eligible for participation), or have elevated liver enzyme measurements, as determined by the central laboratory at screening (Visit 1):
  - Total bilirubin >2x ULN, with the exception of previously diagnosed Gilbert's syndrome
  - ALT or serum glutamic pyruvic transaminase (SGPT) >3x ULN, or
  - AST or serum glutamic oxaloacetic transaminase (SGOT) >3x ULN, or
  - ALP >2.5x ULN.

***Renal***

23. Have a history of renal transplantation, are currently receiving renal dialysis, or have an estimated glomerular filtration rate <30 mL/min/1.73 m^2, calculated by the Chronic Kidney Disease-Epidemiology equation, as determined by the central laboratory at screening (Visit 1).

***Hematologic***

24. Have had a blood transfusion or severe blood loss within 90 days prior to screening (Visit 1).
25. Have known hemoglobinopathy, hemolytic anemia or sickle cell anemia, or any other traits of hemoglobin abnormalities known to interfere with the measurement of HbA1c in the opinion of the investigator.

***Malignancy***

26. Have a history of an active or untreated malignancy or are in remission from a clinically significant malignancy within 5 years prior to screening (Visit 1).

**Exceptions:**

- Basal cell or squamous cell skin cancer.

27. Are at increased risk for developing cancer or a recurrence of cancer.

***General***

28. Have known hypersensitivity or allergy to any of the study medications or their excipients.
29. Have any other serious disease or condition (for example, known drug or alcohol abuse or psychiatric disorder) that, in the opinion of the investigator, would pose a significant risk to the study participant, or preclude the study participant from following and completing the protocol.
30. Have evidence of current or recent, within 6 months timeframe, history of any substance use disorder(s) of any severity as defined by the DSM-5 in the opinion of the investigator, excepting disorders of nicotine or caffeine use.
31. Have had a significant weight gain or loss in the past 3 months in the investigator's opinion (for example,  $\geq 5\%$ ).
32. Persons of childbearing potential who
  - are pregnant or intend to become pregnant
  - are lactating/breastfeeding (including the use of a breast pump)
  - are unwilling to remain abstinent or use birth control, or
  - test positive for pregnancy at the time of screening.

***Prior or concomitant therapy***

33. Have received any of the following nonallowed diabetes medication within prior 90 days including

- meglitinides (glinides)
- sulfonylureas
- pramlintide
- alpha-glucosidase inhibitors, or
- thiazolidinediones.

34. Are receiving chronic or received systemic glucocorticoid therapy for >14 days within the 30 days before screening (Visit 1).

**Exceptions:**

- replacement therapy for adrenal insufficiency
- topical, intraocular, intranasal, or inhaled preparations, or
- intra-articular injection.

**Prior or concurrent clinical study experience**

35. Are currently enrolled in any other clinical study involving an IP or any other type of medical research, judged not to be scientifically or medically compatible with this study.

36. Have participated, within the last 30 days in a clinical trial involving an IP. If the previous IP has a long half-life, 3 months or 5 half-lives (whichever is longer) should have passed.

37. Have previously completed or withdrawn from this study after having signed the informed consent form (ICF) or any other study investigating LY3209590 after receiving at least 1 dose of the study basal insulin.

38. Are investigator site personnel directly affiliated with this study and/or their immediate families. Immediate family is defined as a spouse, parent, child, or sibling, whether biological or legally adopted.

39. Are Eli Lilly and Company employees or are employees of any third party involved in the study who require exclusion of their employees.

### **5.3. Lifestyle Considerations**

**Diabetes management counseling**

Qualified study personnel will provide diabetes management counseling, which will include instructions on diet and exercise and education about the signs, symptoms, and treatment of hypoglycemia, should it occur. Diabetes self-management counseling should be reviewed throughout the study, as needed.

***Dietary and exercise considerations***

Study participants should generally follow a healthy meal plan and continue their usual exercise habits throughout the course of the study.

***Dietary and exercise restrictions***

Study participants should not initiate an intensive diet/exercise program with the intent of reducing body weight at any time during the study, other than the lifestyle and dietary measures for diabetes treatment.

**Blood donation**

Study participants should not donate blood or blood products during the study or for 4 weeks following their last study visit.

**5.4. Screen Failures**

A screen failure occurs when a participant who consents to participate in the clinical study is not subsequently randomly assigned to LY3209590 or insulin glargine. A minimal set of screen failure information is required to ensure transparent reporting of screen failure participants to meet the Consolidated Standards of Reporting Trials (CONSORT) publishing requirements and to respond to queries from regulatory authorities. Minimal information includes demography, screen failure details, eligibility criteria, and any SAE.

Individuals who do not meet the criteria for participation in this study (screen failure) will not be rescreened.

**5.5. Criteria for Temporarily Delaying Enrollment of a Participant**

This section is not applicable for this study. All entry criteria must be met within the specified intervals in the SoA.

## 6. Study Intervention(s) and Concomitant Therapy

Study intervention is defined as any investigational intervention(s), marketed product(s), placebo, or medical device(s) intended to be administered to/used by a study participant according to the study protocol.

Investigators and other study personnel are expected to treat participants according to the nationally established standards of care for diabetes management in respective participating countries, except when that treatment would be in conflict with the protocol-provided treatment requirements. If there are no local/national standards of care for diabetes, the investigators should follow current published standards of care from the American Diabetes Association (ADA 2022).

### 6.1. Study Intervention(s) Administered

This table lists the interventions used in this clinical study.

Intervention Name	LY3209590	Insulin glargine	Insulin lispro
Dose Formulation	Solution	Solution	Solution
Unit Dose Strength(s)	500 units/mL	100 units/mL	100 units/mL
Dosage Level(s)	Individualized dosing (see Section 6.5.1)	Individualized dosing (see Section 6.5.2)	Individualized dosing (see Section 6.5.3)
Route of Administration	Subcutaneous injection	Subcutaneous injection	Subcutaneous injection
Frequency of Administration	Once-weekly study basal insulin	Once-daily study basal insulin	Background prandial insulin therapy with meals and as needed
Authorized as defined by EU Clinical Trial Regulation	Not authorized in EU	Authorized and used according to authorization	Authorized and used according to authorization

#### LY3209590 frequency of administration and guidance for missed doses

LY3209590 should be administered once weekly at approximately the same time and day each week.

If a dose is missed, it should be administered as soon as possible if at least 3 days (72 hours) remain until the next scheduled dose. If less than 3 days remain before the next scheduled dose,

skip the missed dose and administer the next dose on the regularly scheduled day. In each case, participants can then resume their regular once-weekly dosing schedule.

The day of weekly administration can be changed, if necessary, only if the last dose has been administered at least 3 days earlier.

### **Insulin glargine frequency of administration**

Insulin glargine should be administered daily at approximately the same time each day.

### **Anatomical location of injections**

For both LY3209590 and insulin glargine, participants should rotate injection sites from one injection to the next, even when injecting within the same region. Injections may be administered in the abdomen, thigh, arm, or buttock.

### **Packaging and labeling**

Study interventions will be supplied by the sponsor or its designee in accordance with current Good Manufacturing Practice. Study interventions will be labeled as appropriate for country requirements.

#### **6.1.1. Medical Devices**

LY3209590 or insulin glargine, and insulin lispro will be provided in prefilled pen injectors.

Instructions for device use will be provided.

All Product Complaints, including malfunction, use error and inadequate labeling, shall be documented and reported by the investigator throughout the clinical investigation (see Section 8.3) and appropriately managed by the sponsor.

#### **6.1.2. Background Therapy**

For patients with type 2 diabetes requiring MDI therapy, standard of care stipulates treatment with both basal and prandial bolus insulin. In this study, participants will be treated with LY3209590 or insulin glargine as study basal insulin intervention and insulin lispro as prandial bolus therapy.

Insulin lispro is being used to standardize the prandial insulin therapy.

#### **6.1.3. Rescue Therapy for Management of Participants with Severe, Persistent Hyperglycemia during the Treatment Period**

Participants in this clinical trial will be treated with basal insulin, that is, LY3209590 or insulin glargine, both in combination with prandial insulin lispro. Correction doses of insulin lispro can also be used.

An additional antihyperglycemic medication should be considered as rescue therapy if a participant develops severe, persistent hyperglycemia after randomization, based on meeting one of the criteria in this table, and in the absence of intercurrent cause of the hyperglycemia.

Average Fasting Glucose over 2-week Period	Timing of Events
>270 mg/dL (15 mmol/L)	From Visit 15 until Visit 17 (Weeks 12 to 16)
>240 mg/dL (13 mmol/L)	After Visit 17 until Visit 19 (Weeks 16 to 20)
>200 mg/dL (11 mmol/L)	After Visit 19 until Visit 23 (Weeks 20 to 26)

Investigators should first confirm that the participant is fully compliant with the assigned therapeutic regimen and that the participant does not have an acute condition causing severe hyperglycemia. If study basal and prandial insulin therapy are fully optimized, the investigator will decide, in consultation with the participant, on an appropriate intensification of therapy after considering relevant clinical criteria. Therapy intensification may include adjustment of concomitant antihyperglycemic medication, addition of a concomitant antihyperglycemic medication if taking <3 concomitant medications as per Section 6.8.3, or addition of a non-study insulin. Participants who receive a new intervention for hyperglycemia management should also continue administering study insulin therapy for the remaining period in the trial.

Participants who require a new non-study basal insulin intervention as rescue therapy for hyperglycemia management must discontinue study basal insulin therapy (LY3209590 or insulin glargine). The participant will remain in the study and follow procedures for the remaining study visits.

The investigator should ensure that the participant met the criteria for severe or persistent hyperglycemia before initiating rescue medicine and document this in the source files.

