### 6.5.1.2. LY3209590 Dose Adjustment

From Visit 5 until the end of treatment (Week 26), assess hypoglycemia events over the previous week, and reduce the LY3209590 dose if the participant meets a criterion for hypoglycemia dose reduction according to the table below.

Hypoglycemia Dose Reduction Criteria	Decrease the LY3209590 dose:
1 nocturnal hypoglycemia event $\leq 70$ mg/dL (3.9 mmol/L) a	to previous lower dose b
1 fasting hypoglycemia event $\leq 70$ mg/dL (3.9 mmol/L) a	by 20 to 40 units or as clinically indicated
Any confirmed severe hypoglycemia event	by 20 to 40 units or as clinically indicated

a Investigator should use discretion to adjust for daytime hypoglycemia that is not attributed to prandial insulin.

b If there is no previous lower dose, then decrease basal insulin dose by 10% or as clinically indicated and round dose to the nearest 10 units.

If the participant does not meet criteria for hypoglycemia dose reduction, determine the median fasting glucose and adjust the LY3209590 dose according to the table below.

This table provides guidance for dose adjustments based on median FBG from the 3 most recently recorded FBG data from the previous week. Subject with lead-in FBG values  $\leq 120$  mg/dL or  $\leq 6.6$  mmol/L may be titrated with the more gentle titration algorithm throughout the study.

LY3209590 Dose Adjustment		
Median FBG mg/dL (mmol/L)	Median Lead-In FBG $\leq 120$ mg/dL (6.6 mmol/L) a	Median Lead-In FBG $> 120$ mg/dL (6.6 mmol/L)
<80 (4.4)	-10 to -20 units	-20 units
80–120 (4.4–6.6)	No change	No change
121–140 (6.7–7.7)	+10 units	+20 units
>140 (7.7)	+20 units	+40 units

Abbreviations: FBG = fasting blood glucose.

a Investigators may choose the more gentle titration algorithm for subjects with a pre-study basal insulin dose  $< 20$  units and median FBG  $> 120$  mg/dL (6.6 mmol/L)

Note: 120 mg/dL is rounded to 6.6 mmol/L and 121 mg/dL is rounded to 6.7 mmol/L to allow for distinct thresholds in consideration of glucose meters only displaying 1 significant digit after the decimal point.

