### 6.5.2.2. Insulin Glargine Dose Adjustment

For Visit 4 until end of treatment (Week 26), assess hypoglycemia events over the previous week, and reduce the insulin glargine dose if the participant meets criterion for hypoglycemia dose reduction according to this table.

Hypoglycemia Dose Reduction Criteria	Decrease the glargine dose:
1 nocturnal hypoglycemia event $\leq$ 70 mg/dL (3.9 mmol/L) a	to previous lower dose b
1 fasting hypoglycemia event $\leq$ 70 mg/dL (3.9 mmol/L) a	
Any confirmed severe hypoglycemia	by 3 to 6 units or as clinically indicated

a Investigator should use discretion to adjust for daytime hypoglycemia that is not attributed to prandial insulin.

b If there is no previous lower dose, then decrease basal insulin dose by 10% or as clinically indicated.

If the participant does not meet criteria for hypoglycemia dose reduction, determine the median fasting glucose and adjust the insulin glargine dose according to this table. This table provides guidance for dose adjustments based on median FBG from the 3 most recently recorded FBG data from the previous week.

Insulin Glargine Dose Adjustment		
If the median FBG is...		Then...
mg/dL	mmol/L	
<80	<4.4	reduce the dose by 3 U.
80-120	4.4-6.6	do not change the dose.
121-140	6.7-7.7	increase the dose by 3 U.
>140	>7.7	increase the dose by 6 U.

Abbreviations: FBG = fasting blood glucose; U = units.

Note: 120 mg/dL is rounded to 6.6 mmol/L and 121 mg/dL is rounded to 6.7 mmol/L to allow for distinct thresholds in consideration of glucose meters only displaying 1 significant digit after the decimal point.

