### 6.6.1. Glucose in Target Ranges, Hypoglycemia or Hyperglycemia

The following variables of time in range, hypoglycemia, hyperglycemia during each CGM session will be derived:

- Percentage and Duration (in minutes) of time per day where glucose values are within a hypoglycemic range (defined as  $<54$  mg/dL [3.0 mmol/L]) during the nighttime period (defined as midnight to 0600 hours), the daytime period (defined as 0600 hours to 2400 hours) and a 24-hour period.
- Percentage and Duration (in minutes) of time per day where glucose values are within a hypoglycemic range (defined as  $<70$  mg/dL [3.9 mmol/L] and  $\geq 54$  mg/dL [3.0 mmol/L]) during the nighttime period, the daytime period, and a 24-hour period.
- Percentage and Duration (in minutes) of time per day where glucose values are within a hypoglycemic range (defined as  $<70$  mg/dL [3.9 mmol/L]) during the nighttime period, the daytime period and a 24-hour period.
- Percentage and Duration (in minutes) of time per day glucose values are within a hyperglycemic range (defined as  $>180$  mg/dL [10.0 mmol/L] and  $\leq 250$  mg/dL [13.9 mmol/L]) during the nighttime period, the daytime period and a 24-hour period.
- Percentage and Duration (in minutes) of time per day glucose values are within a hyperglycemic range (defined as  $>250$  mg/dL [13.9 mmol/L]) during the nighttime period, the daytime period and a 24-hour period.
- Percentage and Duration (in minutes) of time per day glucose values are within a hyperglycemic range (defined as  $>180$  mg/dL [10.0 mmol/L]) during the nighttime period, the daytime period and a 24-hour period.
- Percentage and Duration (in minutes) of time per day glucose values are within a glucose range (defined as between 70 mg/dL and 180 mg/dL [3.9 and 10.0 mmol/L]) inclusive during the nighttime period, the daytime period and a 24-hour period.
- Percentage and Duration (in minutes) of time per day glucose values are within a glucose range (defined as between 70 mg/dL and 140 mg/dL [3.9 and 7.8 mmol/L] inclusive) during the nighttime period, the daytime period and a 24-hour period.

The percentage of time within a glucose range (target, hypoglycemia, or hyperglycemia ranges) will be calculated as the number of observations within the specified range divided by the

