number of observations in the time interval (for example, 24-hour period). The average percentage of time among valid CGM days for the corresponding time interval during each CGM session will be used in the analysis.

The duration (in minutes) within the glucose range will then be calculated as the average percentage of time within the glucose range times the length of the period (24-hour, 18-hour, and 6-hour, for the periods of 24-hour, daytime or nighttime, respectively).

According to the guidance (Battelino et al. 2019), the following CGM targets of glycemic control will also be derived during a 24-hour period.

- The percentage of time within a normal glucose range (defined as between 70 mg/dL and 180 mg/dL [3.9 and 10.0 mmol/L] inclusive) >70%
- The percentage of time within a hypoglycemia range (defined as <70 mg/dL [3.9 mmol/L]) <4%
- The percentage of time within a hypoglycemia range (defined as <54 mg/dL [3.0 mmol/L]) <1%
- The percentage of time within a hyperglycemic range (defined as >180 mg/dL [10.0 mmol/L]) <25%
- The percentage of time within a hyperglycemic range (defined as >250 mg/dL [13.9 mmol/L]) <5%

In addition, according to the guidance in 2023 (Battelino et al. 2023), 2 composite endpoints will be derived during a 24-hour period:

- >70% time in range 70 -180 mg/dL (3.9 - 10.0 mmol/L inclusive) and <4% time below range <70 mg/dL (<3.9 mmol/L)
- >70% time in range 70 -180 mg/dL (3.9 - 10.0 mmol/L inclusive) and <1% time below range <54 mg/dL (<3.0 mmol/L)

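### Two of the three rescue cut-offs in Protocol 6.1.3 pair mg/dL and mmol/L values that are not the same glucose, and no governing unit is named

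*Protocol*

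**What the plan says.** The table in Protocol 6.1.3 gives three cut-offs for average fasting glucose over a two-week period:

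- Weeks 12 to 16: ">270 mg/dL (15 mmol/L"
- Weeks 16 to 20: ">240 mg/dL (13 mmol/L"
- Weeks 20 to 26: ">200 mg/dL (11 mmol/L"

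The section names no governing unit and has no rounding note. It asks the investigator to consider rescue, to check compliance and rule out an acute cause first, and to intensify only once study insulin is fully optimized. It also asks the investigator to make sure the criteria were met before rescue begins and to record this in the source files.

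SAP Section 3 makes the start date of the first rescue treatment one of the dates that can end a participant's EAS2 data. EAS1, used for the treatment regimen estimand, keeps all measurements regardless of rescue.

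For basal titration, Protocol 6.5.1.2 has a row "121–140 (6.7–7.7", and Protocol 6.5.2.2 uses the same limits. A note under both tables says "120 mg/dL is rounded to 6.6 mmol/L and 121 mg/dL is rounded to 6.7 mmol/L to allow for distinct thresholds", because meters show one decimal. It does not mention 140 mg/dL.

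**The concern.** The two values in a row should describe one glucose level, because a site may work in either unit. If they do not, the same two-week average can satisfy the printed criterion in one unit and fail it in the other. The criterion is one the investigator is asked to verify and document, and the start of rescue is one of the two intercurrent events named for the primary estimands. What is at stake is consistent application of the rescue criterion across sites and, through it, which later measurements remain in EAS2.

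**Working it through.** **Conversion factor, from the documents.** Protocol 6.5.3 gives the insulin correction factor as 1800 divided by total daily dose in mg/dL and 100 divided by total daily dose in mmol/L: 1800 / 100 = 18. Other printed pairs agree at one decimal:

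- 54 / 18 = 3.0 (printed 3.0)
- 130 / 18 = 7.2 (printed 7.2)
- 180 / 18 = 10.0 (printed 10.0)
- 250 / 18 = 13.9 (printed 13.9, SAP 6.6.1)

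**Reproducing the printed mmol/L values, then converting them back.**

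| Weeks | Printed mg/dL | mg/dL / 18 | Printed mmol/L | Printed mmol/L × 18 | Gap (mg/dL) |
|---|---|---|---|---|---|
| 12 to 16 | 270 | 15.0 | 15 | 270 | 0 |
| 16 to 20 | 240 | 13.3 | 13 | 234 | 240 − 234 = 6 (6 / 240 = 2.5%) |
| 20 to 26 | 200 | 11.1 | 11 | 198 | 200 − 198 = 2 (2 / 200 = 1%) |

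The printed 13 and 11 are reproduced by rounding to a whole number, but not at the one decimal used for the other thresholds.

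**Effect on the criterion.** A two-week average of 236 mg/dL is 236 / 18 = 13.1 mmol/L. It exceeds 13 mmol/L but not 240 mg/dL. In whole mg/dL, 235 through 240 are discordant in the second row, and 199 and 200 in the third.

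**Sensitivity to the factor.** With 18.016 or 18.018 (assumed alternatives, not in the documents), 13 mmol/L becomes 234.2 mg/dL and 11 mmol/L becomes 198.2 mg/dL. The gaps are then 5.8 and 1.8 mg/dL, so the finding does not depend on using exactly 18.

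**Could rounding the average remove it?** If a site rounded the average to a whole number before comparing, a result above 13 would need at least 13.5 mmol/L, and 13.5 × 18 = 243 mg/dL. The discordance then moves to the other side of 240 and does not disappear.

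**Titration limit, for comparison.** 140 / 18 = 7.78. A display that rounds to one decimal shows 7.8, above the printed 7.7. A display that truncates shows 7.7, and 141 mg/dL (7.83) shows 7.8. Under truncation the mg/dL and mmol/L limits agree.

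**The case against.** The strongest reply is that nothing was miscalculated. The mg/dL value comes first, and 15, 13 and 11 are each its correct whole-number rounding. That stands as an explanation of the origin. It does not settle the use, because a rounded value printed as a strict cut-off, with no statement that mg/dL governs, can be applied as written.

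A second reply is that crossing the cut-off triggers nothing automatically. Rescue is only to be considered, after other checks, and two sites using the same unit could already decide differently at the same glucose. This also stands, and it limits the consequence to eligibility within two narrow bands. A reader might infer that the same glucose is an intercurrent event at one site and not at another. The documents do not support that: the intercurrent event is the initiation of rescue, and the EAS2 cut-off is the date rescue starts.

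A reader might also infer that the titration tables give a doubled dose step for the same reading. SAP 6.6.1 prints the range "between 70 mg/dL and 140 mg/dL [3.9 and 7.8 mmol/L] inclusive", while the protocol ends the middle titration row at 140 mg/dL with 7.7 mmol/L. In the next row the glargine instruction is "increase the dose by 6 U" instead of 3 U, and the LY3209590 step is +40 instead of +20 units, or +20 instead of +10. This is not established:

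- It requires a meter that rounds, and the documents do not say how the meter forms its decimal.
- The printed 120/6.6, 121/6.7 and 140/7.7 all fit truncation to one decimal, under which the conflict at 140 vanishes.
- The SAP's 7.8 is a boundary for CGM analysis, not a glucometer dosing threshold.
- On a rounding meter the discordant band would still be only about 1 mg/dL: 7.8 shows from 7.75 × 18 = 139.5, and 140 shows up to 140.5.
- The tables are guidance, and the prescribed dose is the investigator's responsibility.

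The 120/6.6 pair is a declared convention and is not counted against the plan.

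**Conclusion.** The point holds for two rescue rows in Protocol 6.1.3. At 18 mg/dL per mmol/L, averages above 234 and up to 240 mg/dL (Weeks 16 to 20), or above 198 and up to 200 mg/dL (Weeks 20 to 26), meet the mmol/L criterion and fail the mg/dL one. This assumes that each printed value is applied as written to an unrounded average.

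The direct effect is on eligibility for rescue. The analysis is touched only if rescue is then started, and only through the EAS2 cut-off and the efficacy estimand. The documents give no distribution of fasting glucose, so the number affected cannot be calculated. It is likely to be small, given the width of the bands and the other conditions for rescue. Power and alpha are unchanged.

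Bias between arms should not be inferred. The documents do not say which unit each site uses. If the unit follows country (an assumption), both arms within a country share it, and country is a stratification factor.

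The titration point is conditional: it is a question for the sponsor about meter display, not a demonstrated conflict. Overall this is a minor clarification worth making.

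**What to change.** Reconcile the mg/dL and mmol/L values in the Protocol 6.1.3 table so that each row describes one glucose level, or state which unit governs. The sponsor must say which printed value was intended; this review does not choose between them. In the same clarification, confirm whether the rounding note in 6.5.1.2 and 6.5.2.2 also covers 140 mg/dL printed as 7.7 mmol/L, and state how the study meter forms its one-decimal display.

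The cost is a protocol clarification and a note to sites. The SAP already plans a listing of participants who receive rescue therapy (4.6.2.1.10), and the unit applied could be added to it. No analysis method or sample size changes.
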